13.7.2 Missing Data

Mixed-effect models assume that data is missing at random (MAR) and uses the correlation of withinsubject observations to adjust for any missing outcome data. Therefore, participants will be included in the primary analysis model if they have completed the PEM Hand Health Profile for at least one follow-up timepoint and they have data for all baseline covariates within the model.

If the overall proportion of participants not included within the primary model, due to missing outcome data at all time points or missing baseline covariates, is greater than 5%, the impact of missing data on the primary analysis will be assessed using multiple imputation by chained equations. The imputation model will include key baseline variables (age, sex, digital nerve injury, anaesthetic type, baseline PEM Hand Health Profile score and baseline EQ5D-5L score).

A 'burn –in' of 150 will be used and 50 imputed datasets will be created. The primary analysis will then be rerun within the imputed datasets and Rubin's rules will be used to combine the multiply imputed estimates.

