5.5 Statistical Considerations

5.5.1 Method of Randomisation

Eligible participants will be randomly allocated in a 1:1 ratio to either the intervention (repair of FDS only) or control (repair of both FDS and FDP) group, using block randomisation stratified by study site with randomly varying block sizes. An independent statistician at YTU, who is not involved in the recruitment of participants, will generate the allocation schedule. The allocation schedule will be generated in STATA v 17 or later.

Randomisation will be completed in theatre and treatment will be allocated on an individual patient basis.

Randomisation will be carried out using REDCap.

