5.5.2 Determination of Sample Size

There will be a 22-month recruitment period for the FLARE trial. The total target sample size will be 310 participants.

A six-point difference on the Patient Evaluation Measure (PEM) represents the threshold at which treatment differences become important (based on observational data from patients with Dupuytren's contracture for the DISC trial (HTA 15/102/04)). However, recent analysis within a flexor tendon population has found a seven-point difference on the PEM to be important and thus represents an appropriate non-inferiority margin to be used in this population. For 90% power and alpha=0.025, 310 participants are required to establish noninferiority within a margin of 7 points on the PEM (SD=17; upper 80% confidence limit (22)), based on the lower limit of a 95% two-sided confidence interval (equivalent to a one-sided 97.5% CI) and 20% attrition.

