13.5 Primary analysis

The primary outcome measure (PEM Hand Health Profile) will be reported descriptively, by trial arm and overall, for all data collection timepoints (baseline, six-weeks, three-months and six-months postrandomisation).

The primary analysis will compare PEM Hand Health Profile scores between treatment groups using a covariance pattern mixed effect linear model, incorporating data from all post-randomisation time points (six-weeks, three-months and six-months). The model will adjust for digital nerve injury, anaesthetic type, baseline PEM Hand Health Profile score (both pre and post-injury), time, treatment arm, treatment-by-time interaction as fixed effects, with site and participant as random effects to account for clustering by site and repeated observations per participant.

The correlation of observations within participants over time will be modelled by a covariance structure. The different covariance structures for repeated measurements that are available as part of the analysis software will be applied to the model. The Akaike information criterion will be used to compare models specifying different covariance structures with smaller values preferred. Model assumptions will be checked as follows: the normality of the standardised residuals will be assessed using a QQ plot, and homoscedasticity will be assessed by means of a scatter plot of the standardised residuals against fitted values. One possible violation of the assumptions may be the normality of the residuals due to a potential ceiling or floor effect where a lot of patients have a score of zero. In this instance, we will carry out an additional sensitivity analysis using a semi-parametric approach based on an ordinal regression model using the 'glm' Stata command with a logit link function.

Participants will only be included in the model if they have complete data for the baseline covariates and a valid PEM Hand Health Profile score for at least one post-randomisation timepoint.

The treatment effect at all time points (six-weeks, three-months and six-months) and overall will be extracted in the form of an adjusted mean difference, two-sided 95% CIs (equivalent to a one-sided 97.5% CI) and p-value. The primary timepoint of interest is six-months post-randomisation. A detailed description of how we will interpret the treatment effect estimate is included in Appendix A.

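### The imputation model in SAP 13.7.2 does not name the randomised arm; run as listed, this conditional sensitivity analysis shrinks the treatment difference

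*SAP*

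**What the plan says.** SAP 13.5 defines the primary model. Its fixed effects include arm, time and arm-by-time, with site and participant as random effects. Entry is restricted: "Participants will only be included in the model if they have complete data for the baseline covariates", and at least one valid follow-up score is also needed.

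SAP 13.7.2 sets the trigger for imputation: "If the overall proportion of participants not included within the primary model, due to missing outcome data at all time points" or because of missing baseline covariates, exceeds 5%. Chained equations then produce 50 imputed datasets, the primary analysis is rerun in each, and Rubin's rules combine the results. The content of the imputation model is given in one sentence: "The imputation model will include key baseline variables (age, sex, digital nerve injury, anaesthetic type", and then "baseline PEM Hand Health Profile score and baseline EQ5D-5L score". The list ends there. Neither document adds arm, imputation by arm, or the follow-up PEM scores to it.

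**The concern.** An imputation model should contain the terms that the later analysis estimates. Here the arm effect, which the rerun exists to estimate, is missing from the list. A participant with no follow-up PEM score would be imputed from baseline variables alone, so the expected outcome would not depend on arm. Adding such participants to the analysis pulls the estimated difference toward zero.

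In a non-inferiority trial that pull matters. SAP 13.7.1 itself warns that bias toward the null can produce false claims of non-inferiority. The imputation is the only planned sensitivity analysis for missing data that yields a treatment estimate, so the harm would be a robustness check that reassures when it should not.

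**Working it through.** **Inputs from the documents.** Margin and SD: "margin of 7 points on the PEM (SD=17; upper 80% confidence limit (22"; power and alpha: "For 90% power and alpha=0.025, 310 participants are required"; attrition: "equivalent to a one-sided 97.5% CI) and 20% attrition" (all Protocol 5.5.2). Allocation: "Eligible participants will be randomly allocated in a 1:1 ratio" (Protocol 5.5.1). Trigger of 5% and 50 imputations: SAP 13.7.2.

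**Assumptions not in the documents.** Correlation of 0.4 between baseline and six-month PEM; outcomes missing completely at random; a six-month ANCOVA in place of the mixed model; a residual correlation of 0.6 where an earlier visit is used. Differences are coded so that positive means FDP-only is worse.

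**1. The plan's sample size.** Per arm: 2 × (1.95996 + 1.28155)² × 17² / 7² = 2 × 10.507 × 289 / 49 = 123.9, so 124. Total 248; 248 / 0.80 = 310. This matches. An SD of 22 would give 208 per arm and 416 / 0.80 = 520, so 310 rests on SD 17, which is used below.

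**2. When the check runs.** 15 / 310 = 4.8% and 16 / 310 = 5.2%, so at the planned size 16 excluded participants trigger it.

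**3. Expected dilution.** Let f be the fraction with no follow-up score. Observed participants contribute the true difference and imputed ones contribute none: expected estimate = (1 − f) × 7 + f × 0. This gives 0.95 × 7 = 6.65, 0.90 × 7 = 6.30 and 0.80 × 7 = 5.60.

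**4. Simulation at a true difference of 7.** 1,500 trials per row, 310 participants, 50 imputations, Rubin's rules. Non-inferiority is claimed if estimate + 1.96 × SE < 7.

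| Fully missing | Expected | Arm not in imputation: mean, false claims | Arm in imputation: mean, false claims |
|---|---|---|---|
| 5% | 6.65 | 6.66, 2.9% | 7.02, 2.2% |
| 10% | 6.30 | 6.24, 3.9% | 6.94, 2.6% |
| 20% | 5.60 | 5.55, 6.3% | 6.95, 2.5% |

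A second run (3,000 trials, 20 imputations) gave 6.6, 6.3 and 5.6 with 3.0%, 3.8% and 6.5% false claims. With arm included it gave 7.0 to 7.1 and 1.9% to 2.7%.

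Monte Carlo error in the table is √(0.025 × 0.975 / 1500) = 0.4 points near 2.5% and √(0.063 × 0.937 / 1500) = 0.6 points near 6.3%. The error rate at 5% missing is therefore not clearly above nominal; the rate at 20% is.

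**5. Check of the 20% row.** Without arm, the average estimated SE was 1.97 and the empirical SE 1.59. A claim needs an estimate below 7 − 1.96 × 1.97 = 3.14. (3.14 − 5.55) / 1.59 = −1.52, a probability of about 6.4%. With arm: 7 − 1.96 × 1.99 = 3.10; (3.10 − 6.95) / 1.98 = −1.94, about 2.6%. Both agree with the simulation.

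**6. Who is affected.** Arm absent throughout, at 5% / 10% / 20% missing:
- All three visits missing, with the visits imputing one another (500 trials, 10 imputations): 6.58 / 6.29 / 5.55. Adding arm gave 7.09 / 7.00 / 7.14.
- Six-month score missing, but an earlier score observed and used: 6.89 / 6.67 / 6.41; false claims 2.3% / 2.7% / 3.3%.
- Only a baseline covariate missing, outcomes observed (1,500 trials): 6.91 / 6.94 / 6.75; false claims 2.9% / 2.0% / 3.3%.

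**7. True difference of zero.** Mean estimates without arm were −0.09, −0.03 and 0.07; with arm, −0.09, −0.03 and 0.08. There is no bias.

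**The case against.** The best defence is that the sentence says which baseline variables enter and does not claim to be complete. An analyst could add arm, and chained equations normally let the PEM visits predict one another. That is fair as a reading of intent. However, nothing requires arm to be added, in a section precise enough to fix the burn-in and the number of imputations. Chaining the visits helps only people with at least one score. The outcome part of the trigger concerns people with none, and for them the dilution is essentially complete (step 6).

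Four limits on the point do stand:
- A reader might infer that the trial's own false-positive rate rises to 6%. The documents do not support this. The non-inferiority decision comes from the SAP 13.5 model, which contains arm; the imputation is secondary and conditional.
- A reader might infer that the bias always favours FDP-only. It does so only if FDP-only is truly worse. If FDP-only were better, shrinkage would work against it.
- A reader might equate the planned 20% attrition with 20% fully missing. Protocol 5.5.2 does not say that, and some of those lost by six months may have earlier scores. The 20% row is an upper scenario.
- A reader might also call the trigger itself wrong, because it ignores a missing six-month score when an earlier one exists. SAP 13.7.2 gives its reason: the mixed model already uses such people under missing at random. A wider trigger is a preference. It is true that imputation under the same assumption tests no departure from it, but that is a case for an addition and does not show an error.

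**Conclusion.** The gap is real but confined. As listed, the SAP 13.7.2 imputation omits the arm. For participants with no follow-up PEM score, it shrinks a true 7-point deficit to about 6.6, 6.3 or 5.6 at 5%, 10% or 20% fully missing. The one-sided error of that check becomes about 3%, 4% or 6% instead of 2.5%.

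The proportional shrinkage follows from the structure of the model. The error rates rest on the assumed baseline correlation, data missing completely at random and the simplified six-month analysis. The dilution is much smaller for people with an earlier score or with only a baseline covariate missing. The primary result is untouched. What is weakened is the support that the sensitivity analysis could give it, most of all when the true difference lies near the margin.

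**What to change.** State in SAP 13.7.2 that imputation is done separately by randomised arm, or that arm is in every imputation equation. State also that the model contains the PEM Hand Health Profile at six weeks, three months and six months, and both the pre-injury and the post-injury baseline scores, as in the SAP 13.5 model. Site is not essential to this correction: with up to 40 sites, 310 / 40 is about 8 participants per site, so including it needs a feasibility check first.

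Optionally, add a delta-adjusted run for missing six-month PEM, with shifts that the trial team justifies, judged against the 7-point margin. This can be specified only after the scoring direction is reconciled: SAP 7.1 treats higher scores as more disability, while SAP Appendix A treats them as favourable.

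The cost is a sentence or two, an entry in the SAP amendment log (section 14) and a small change to the imputation code. No new data are needed.

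### The multiple-imputation model in SAP 13.7.2 does not name treatment arm, so if the list is followed the only missing-data check on the primary outcome is diluted toward no difference

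*SAP*

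**What the plan says.** SAP 13.7.2 sets a trigger. If the share of participants outside the primary model, "due to missing outcome data at all time points or missing baseline covariates, is greater than 5" per cent, then "the impact of missing data on the primary analysis will be assessed using multiple imputation by chained equations".

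The content of the imputation model is given in one sentence: "The imputation model will include key baseline variables (age, sex, digital nerve injury, anaesthetic type, baseline PEM Hand Health Profile score", with baseline EQ-5D-5L as the last item. All six items are baseline variables. Neither document mentions treatment arm as an imputation variable, or imputation carried out separately by arm. Site and the follow-up PEM scores are not named either.

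The next step is: "The primary analysis will then be rerun within the imputed datasets and Rubin's rules will be used to combine the multiply imputed estimates". The model that is rerun is specified in SAP 13.5 and adjusts for "baseline PEM Hand Health Profile score (both pre and post-injury), time, treatment arm, treatment-by-time interaction as fixed effects", with site and participant as random effects.

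**The concern.** An imputation model should contain at least the terms that the analysis model estimates. Here the list lacks the term of interest. A participant with no follow-up PEM, imputed from baseline variables alone, receives a score drawn from a distribution pooled over the arms. The expected arm difference among such participants is then zero by construction, whatever the true effect.

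In a superiority trial this would be conservative. In a non-inferiority trial, when FDP-only repair is truly worse, it shrinks the deficit and makes non-inferiority easier to show. SAP 13.7.1 raises the same worry about bias toward the null and adds a CACE analysis because of it. The check in the following subsection would introduce that bias itself. Agreement between the imputed and primary results could not then be read as robustness, and a gap between them could be an artefact of leaving arm out.

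**Working it through.** **Inputs from the documents.** Margin 7 points, SD 17, one-sided alpha 0.025, power 90%, attrition 20%, N = 310 (SAP 9; Protocol 5.5.2); 1:1 allocation (SAP 10); upper 80% limit of the SD, 22 (Protocol 5.5.2).

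**Assumptions not in the documents.** Correlation 0.6 between follow-up scores and 0.3 with baseline; the same deficit at every visit; data removed completely at random (a special case of missing at random); one baseline covariate; no site effect; 15 imputations.

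**The plan's own figure.** n per arm = 2 × 17² × (1.960 + 1.282)² / 7² = 578 × 10.51 / 49, which rounds up to 124. Total 248, and 248 / 0.80 = 310. This matches. An SD of 22 would require 520, so the stated N rests on SD 17.

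**Dilution by arithmetic.** Let δ be the true difference and f the fraction with no follow-up PEM. With arm omitted, the expected estimate is (1 − f) × δ + f × 0 = δ(1 − f). For δ = 7:

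- f = 6%: 7 × 0.94 = 6.58
- f = 10%: 7 × 0.90 = 6.30
- f = 20%: 7 × 0.80 = 5.60

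This step needs no correlation assumption.

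**Simulation.** 310 participants and a true deficit equal to the 7-point margin. Chained equations over the three visits were run with and without arm. The six-month score was then analysed with baseline adjustment and pooled by Rubin's rules. Non-inferiority was declared if the 97.5% bound on worsening was below 7. There were 2,000–2,500 trials per row, with Monte Carlo error of about 0.3–0.5 percentage points.

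| Missing pattern | Arm omitted: estimate | Arm omitted: false non-inferiority | Arm included: estimate | Arm included: false non-inferiority |
|---|---|---|---|---|
| 6% no follow-up | 6.61 | 3.2% | 7.03 | 2.4% |
| 10% no follow-up | 6.25 | 3.8% | 6.94 | 2.5% |
| 20% no follow-up | 5.60 | 5.6% | 6.98 | 2.2% |
| 6% no follow-up + 14% missing month 6 only | 6.21 | 3.6% | 6.89 | 2.9% |
| 20% no follow-up, SD 22 | 5.51 | 4.2% | 6.88 | 2.5% |

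A hand check of the third row uses its mean standard error of 2.06 and the empirical SD of the estimate, 1.69. The estimate must fall below 7 − 1.96 × 2.06 = 2.96, and (2.96 − 5.60) / 1.69 = −1.56, a probability of about 5.9%. This is close to the simulated 5.6%.

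**Where the dilution is small or absent.**

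- True difference 0, 20% with no follow-up (600 trials): estimate −0.02 with or without arm.
- FDP-only better by 5, same pattern: the benefit shrinks to 3.96 without arm, against 4.94 with it.
- 6% missing only a baseline covariate, arm omitted: 6.97 and 2.5%.
- 3% missing a covariate plus 3% with no follow-up: 6.73 and 2.1%.
- 10% with no follow-up plus 10% missing month 6 only, chained without arm (1,000 trials, 12 imputations): 6.07 and 4.1%.

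SAP 7.1 treats higher PEM as worse and Appendix A treats it as better. That needs reconciling separately; shrinkage toward zero favours non-inferiority under either coding when FDP-only is worse.

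**The case against.** The strongest reply is that this is a reporting gap and not an error. The sentence says what the model will include and does not say that nothing else enters. Arm is not a baseline characteristic, so a list of key baseline variables need not mention it, and a competent analyst might add it. That stands as far as it goes: the SAP does not exclude arm. But it does not commit to arm either, in a section that goes on to fix the burn-in and the number of imputations.

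Four stronger readings are tempting, and the documents do not support them.

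- **That the trial's own error rate is inflated.** Non-inferiority is judged from the SAP 13.5 model under Appendix A, and that model contains arm and treatment-by-time. The imputation analysis is conditional on the 5% trigger and has no decision rule attached. The rates above belong to this check alone.
- **That participants' own earlier PEM scores are discarded.** The method is chained equations, in which the incomplete visit scores would ordinarily predict one another. Part of the arm difference then passes through for people with some follow-up, as the mixed patterns show. Likewise, the single mention of baseline PEM may cover both the pre- and post-injury scores.
- **That everyone who triggers the analysis contributes to the dilution.** The trigger also counts participants missing only a baseline covariate. Their PEM scores are observed, and imputing a covariate causes almost no dilution.
- **That 20% wholly missing is the expected case.** The 20% is overall attrition. Anyone with a six-week or three-month score and complete covariates stays in the primary model, so the wholly missing fraction should normally be smaller.

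**Conclusion.** The specification is wrong as written: applied as listed, it gives a biased estimate when the true difference is not zero, beyond being short on detail. For participants with no follow-up PEM, the shrinkage is about the wholly missing fraction. At a true deficit of 7 the check would report about 6.6, 6.3 and 5.6 at 6%, 10% and 20% wholly missing, with false non-inferiority of about 3%, 4% and 5–6% against a nominal 2.5%. Just above the trigger the inflation is small relative to Monte Carlo error; the 20% figure is an upper case. The error rates depend on the assumed SD and correlations and on data missing at random.

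The primary result is not affected. The point still matters because no other missing-data check is planned for the primary outcome, and this one would be falsely reassuring precisely when FDP-only repair is worse. It should be fixed, but it does not rank with faults in the primary analysis or its decision rule.

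**What to change.** In SAP 13.7.2, state that the imputation model includes randomised arm, or that imputation is done separately by arm. State also that PEM at six weeks, three months and six months enter as chained variables that predict one another, and that the other covariates of the SAP 13.5 model are included, with both pre- and post-injury baseline PEM named.

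Two matters can be left to the statistician. One is site: with up to 40 sites, 310 / 40 is about 8 participants per site, or about 4 per arm per site, so including site while imputing by arm would be hard to support. The other is extra auxiliary variables such as PRWHE or further surgery.

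The cost is one sentence, recorded in the amendment log in SAP 14, and slightly longer code. No new data are needed and N stays at 310. In the simulations, adding arm brought the estimate back to 6.9–7.0 and the error rate to 2.2–2.9%.

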13.8 Adverse events

Adverse events (AEs) and Serious Adverse Events (SAEs) will be summarised descriptively, by trial arm, and overall. The number of AEs and SAEs per participant will be presented, by treatment group and overall. The event type, expectedness and relatedness to the study treatment of the AEs and SAEs will be summarised similarly.

14. SAP amendment log

Please note all changes that are made to the SAP following initial sign-off in the box below. Include details of the changes made, any notes/justification for these changes, the new version number if applicable, who the changes were made by, and the date.

Amendment/addition to SAP and reason for change	New version number, name and date

15. Signatures of approval

Name	Trial Role	Signature	Date
[name]	Co-Chief Investigator	[name]	28.04.2025
[name]	Co-Chief Investigator	[name]	28.04.2025
[name]	Trial Manager	ter	28.04.2025
[name]	Statistician	[name]	28.04.2025
[name]	Statistician	[name]	28.04.2025
[name]	Senior Statistician	[name]	28.04.2025

16. References

- Schulz, K. F., Altman, D. G., & Moher, D. (2010). CONSORT 2010 Statement: Updated guidelines for reporting parallel group randomised trials. *Journal of Clinical Epidemiology*, 63(8), 834–840. https://doi.org/10.1016/j.jclinepi.2010.02.005
- StataCorp. (2023). Stata Statistical Software: Release 18 (18). Stata Press.

17. Appendices

17.1 Appendix A Accepting non-inferiority

Section 13.5 outlines how we will determine whether repair of FDP only is non-inferior to repair of both FDS and FDP. The primary endpoint is the PEM score at six months. The desired direction of effect is an increase in PEM scores (higher PEM scores are more favourable). When modelling the treatment effect, the treatment allocations will be coded as 1= intervention (repair of FDP only) and 0= control (repair of both FDS and FDP). Therefore, a positive effect will mean the treatment difference will be positive. The non-inferiority margin has been specified as six points and non-inferiority will be accepted if the lower bound of the of the one-sided 97.5% confidence interval for the treatment difference at six months is greater than the non-inferiority margin of -7 points (a 7-point reduction). Figure 1 shows how we will interpret different possible results.

Figure 1: Example scenarios of non-inferiority in the FLARE trial

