4.9 Outcomes

4.9.1 Primary Outcome

The primary outcome will be the Patient Evaluation Measure (PEM) score at six months postsurgery.

PEM is widely used in NIHR funded hand trauma studies and is the main PROM used for flexor tendon injuries in the BSSH UK National Hand Registry. The questionnaire assesses the process of treatment, current state of the hand, and a general assessment. The PEM asks questions relating to symptoms, satisfaction and general disability, which generates a percentage, ranging from 0%-100%, to determine a disability score [24].

PEM will also be collected at baseline, six weeks and three months post-surgery in line with the study assessment schedule (see Table 5)

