7.1 Primary outcome

The primary outcome measure is the Patient Evaluation Measure (PEM) Hand Health Profile completed at baseline, six-weeks, three-months and six-months post-randomisation. The pre-specified primary timepoint of interest is six-months post-randomisation.

The PEM is widely used in National Institute for Health and Care Research (NIHR) funded hand trauma studies and is the main patient reported outcome measure (PROM) used for flexor tendon injuries in the British Society for Surgery of the Hand (BSSH) United Kingdom National Hand Registry. The PEM comprises 19 items and three subscales; Treatment (5-items); Hand Health Profile (11-items) and Overall assessment (3-items). The 11-items which make up the Hand Health Profile subscale will be the primary outcome measure for the FLARE trial.

Items on the PEM Hand Health Profile subscale are measured on seven-point Likert scale such as 1 = Never and 7 = All the time, for example, with questions relating to symptoms, satisfaction and general disability. Scores across the 11-items are summed and used to generate a 0%-100% score to determine an overall disability score, with higher scores indicating greater levels of disability. At baseline the PEM will be collected twice: the first determining the patients Hand Health Profile before they sustained their injury and the second after their injury occurred.

The 11-item PEM Hand Health Profile will not be scored if more than two items are missing. If up to two items are missing, the missing items will be replaced with the mean of the remaining non-missing items.

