13.2 Analysis principles and populations

Analyses will follow the principles of intention-to-treat (ITT) with participant's outcomes analysed according to their original, randomised group, where data are available, irrespective of deviations FLARE Statistical Analysis Plan Version 1.0

based on non-compliance. One-sided 97.5% confidence limits (equivalent to the upper bound of the two-sided 95% confidence interval) will be reported for the primary analysis. There will be no predefined non-inferiority margins for the remaining secondary outcomes, these will be compared for evidence of superiority and two-sided tests at the 5% significance level will be used.

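### SAP Appendix A has the primary outcome running the wrong way, so its acceptance rule would pass FDP-only repair as non-inferior however much worse it is

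*SAP*

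**What the plan says.** **Direction of the scale.** SAP 7.1 sums the 11 Hand Health Profile items into a 0 to 100% score, "with higher scores indicating greater levels of disability". Protocol 4.9.1 agrees, describing a questionnaire "which generates a percentage, ranging from 0%-100%, to determine a disability score". Appendix A (SAP 17.1) says: "The desired direction of effect is an increase in PEM scores (higher PEM scores are more favourable".

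**Contrast and rule.** Appendix A fixes the sign of the contrast: "the treatment allocations will be coded as 1= intervention (repair of FDP only) and 0= control (repair of both FDS and FDP". It continues: "non-inferiority will be accepted if the lower bound of the of the one-sided 97.5% confidence interval for the treatment difference" at six months lies above -7, which it explains as a seven-point reduction. SAP 13.5 sends the reader to Appendix A for the interpretation of the treatment effect, so this is the operative rule.

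**Which bound.** SAP 13.2 describes the reported one-sided limit as "equivalent to the upper bound of the two-sided 95% confidence interval". Protocol 5.5.2 sizes the trial "based on the lower limit of a 95% two-sided confidence interval", and SAP 9 says the same.

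Neither document says that the PEM is reverse-scored before modelling.

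**The concern.** A non-inferiority rule has to limit the chance of accepting a treatment that is worse by the margin or more. On a scale where higher means more disability, with the difference taken as FDP-only minus both, harm is positive and the bound that matters is the upper one. Appendix A instead guards the negative side. In effect it tests whether FDP-only repair is not better by more than 7 points. A seven-point reduction, which Appendix A treats as the limit of acceptable harm, is an improvement on the scale in SAP 7.1.

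This is the trial's only confirmatory comparison; SAP 13.2 sets no margin for any secondary outcome. Applied as written, the rule could turn a clearly unfavourable result into a claim of non-inferiority and deny that claim to a clearly favourable one.

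**Working it through.** **Inputs.** Margin 7, SD 17, 90% power, one-sided alpha 0.025, 20% attrition and N = 310 (Protocol 5.5.2, SAP 9); 1:1 allocation (SAP 10); contrast FDP-only minus both (SAP Appendix A); higher = worse (SAP 7.1).

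**Step 1: reproduce the sample size.**

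n per arm = 2 × 17² × (1.960 + 1.282)² / 7² = 124 after rounding up. Total 248, and 248 / 0.8 = 310, as stated. The SD of 22 that the protocol gives in brackets would need 208 per arm and 520 in total, so 17 is the value used.

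**Step 2: standard error.**

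SE = 17 × √(2/124) = 2.159; the 95% CI half-width is 1.96 × 2.159 = 4.23.

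**Step 3: probability of accepting non-inferiority.** Let d be the true difference, FDP-only minus both, in PEM points; d > 0 means FDP-only is worse.

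- Appendix A (lower bound > -7): P = Φ((d + 7)/SE − 1.96)
- Rule consistent with SAP 7.1 (upper bound < +7): P = Φ((7 − d)/SE − 1.96)

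For example, at d = +7 Appendix A gives Φ(14/2.159 − 1.96) = Φ(4.52) = 0.999997, while the consistent rule gives Φ(−1.96) = 0.025.

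| True d | Appendix A rule | Upper bound < +7 |
|---|---|---|
| -10 | 0.04% | about 100% |
| -7 | 2.5% | 99.9997% |
| -3.5 | 36.7% | 99.8% |
| 0 | 90.0% | 90.0% |
| +3.5 | 99.8% | 36.7% |
| +7 | 99.9997% | 2.5% |
| +10 | about 100% | 0.04% |

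The two columns are mirror images. They agree only at d = 0, which is why the sample size calculation does not reveal the error.

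**Step 4: a single result.** An observed difference of +14 has a 95% CI of 14 ± 4.23, that is 9.77 to 18.23. The whole interval lies beyond 7 points of harm, yet its lower bound is above -7, so Appendix A accepts.

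**Step 5: sensitivity.** With SD 22, SE = 2.794 and acceptance at d = +7 is Φ(14/2.794 − 1.96) = 99.9%. Appendix A also describes the margin as six points; with 6 in place of 7 and SD 17, acceptance at d = +7 is Φ(13/2.159 − 1.96) = 99.998%.

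**The case against.** The strongest reply is that the SAP contradicts itself and a competent analyst would notice. SAP 7.1 has the direction right, SAP 13.2 names the upper bound, and SAP 13.5 requires a second statistician to check the primary analysis. That is fair as a comment on likelihood. But the check is of the analysis, and Appendix A is the only place that states a full acceptance rule. Choosing between two opposite rules after the data are in is what prespecification is meant to prevent.

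A second reply is that the lower limit in Protocol 5.5.2 and SAP 9 is not wrong by itself: with the difference taken as both minus FDP-only, it would be the right bound for a scale where higher is worse. This stands for those two sections, which define no contrast. It does not rescue Appendix A, whose coding excludes that reading.

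Third, acceptance of a worse treatment is a probability, not a certainty: it is 90% at no difference, 99.8% at 3.5 points of harm and above 99.99% from 7 points. The figures also use an unadjusted two-sample standard error, whereas the plan is an adjusted repeated-measures model, and SAP 12 runs the full analysis only if the trial passes its pilot. These points affect the exact percentages or whether the test is reached. They do not change the direction of the error.

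Figure 1 is not visible in the text available here, so whether it repeats the error could not be checked.

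**Conclusion.** The rule in Appendix A is wrong as written and must be corrected. It contradicts the scoring in SAP 7.1 and the disability score in Protocol 4.9.1, and its chance of accepting FDP-only repair rises with harm. With 124 analysed per arm, SD 17 and a normal approximation, the error rate at the 7-point harm boundary is above 99.99% instead of 2.5%. Clear benefit of 7 points would be accepted only 2.5% of the time. The conclusion rests on the PEM being analysed as SAP 7.1 scores it and on the treatment coding in Appendix A; it holds equally at SD 22 or with a 6-point margin. The sample size is unaffected, because the formula is symmetric in sign.

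**What to change.** - **SAP Appendix A.** Replace the rule with: *Higher PEM Hand Health Profile scores are worse. The difference is FDP-only minus FDP and FDS. Non-inferiority is accepted if the upper bound of the two-sided 95% CI at six months is below +7.* In the same edit, remove the mention of a six-point margin, which conflicts with the 7 used in the rule itself, in SAP 9 and in Protocol 5.5.2.
- **Figure 1.** Check it against the corrected rule, and redraw it if it follows the present text.
- **Protocol 5.5.2 and SAP 9.** Change the lower limit to the upper limit, so that both match SAP 13.2 and the coding in Appendix A.
- **SAP 13.5 and Table 18.** State which null hypothesis the p-value tests; neither place does so now. For the primary comparison it should be the one-sided p-value against a difference of +7 or more, not a test of zero difference.

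The cost is an entry in the SAP amendment log, possibly a redrawn figure, and a one-word protocol correction. N stays at 310 and no patients or data are affected. With the corrected rule, acceptance is 2.5% at d = +7 and power is 90% at d = 0, as designed. The change should be made before anyone sees outcome data by arm.
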